3.1.1 Screening/enrollment period (Visit 1, Days -42 to -1)

The screening and enrollment period will be up to 42 days (Days -42 to -1) prior to Day 1 (randomization) of the treatment period. Note, the assessments to be performed during the screening visit can be completed over 2 days if agreed upon with medical advisor.

Eligible patients (aged 18 to 70 years inclusive), will meet a DSM-IV-TR ([American Psychiatric Association 2000](#)) criteria for a diagnosis of MDD, single episode (296.2x) or MDD, recurrent (296.3x) as confirmed by the MINI. At the screening visit, patients meeting preliminary eligible criteria will undergo all study procedures and assessments, including safety evaluations, listed in [Table 4](#) in the manner and sequence specified in [Section 6.2.1.1](#). Assessments will be conducted to ensure that the patient's HAM-D-17 is ≥ 24 , CGI-S is ≥ 5 , and QIDS-SR-16 is ≥ 19 . Psychiatric history and a brief screening for family psychiatric history will be administered as well. If the screening and randomization visits are < 7 days apart, a repeat serum pregnancy test is not required; however, negative urine pregnancy tests are required prior to each dose of IP.

If the patient qualifies for enrollment based on the inclusion/exclusion criteria (including HAM-D-17 ≥ 24 , CGI-S ≥ 5 , and QIDS-SR-16 ≥ 19), the patient will return to the study site for reconfirmation of inclusion criteria, and if still eligible, randomization and after baseline MADRS, HAM-A, S-STS and CogState, the first infusion (Visit 2). If the patient does not meet these criteria, the patient will be considered a screen failure and will not be enrolled.

Patients will continue on their existing antidepressant medication during the study. The list of permitted antidepressants and dual-therapy combinations during the study is given in [Table 2](#) and [Table 3](#). Other treatments that are prohibited, allowed with restrictions, or permitted, are listed in [Table 6](#). The screening period (from Visit 1 to Visit 2) may take up to 42 days to allow the investigator time to obtain treatment history reports in support of the ATHF and also to review the results of laboratory assessments (which may confound the results of the study and to ensure the safety of patients).

3.1.2 Randomization/double-blind treatment period (Weeks 1 to 12)

Patients will undergo all procedures and assessments at the designated visits per the study assessments ([Table 4](#)); visits are as follows:

Week 1: Visits 2, 3, and 4 (Days 1 to 7, Infusions 1 to 3)

Only qualified patients will be randomized (Visit 2, Day 1).

Patients will undergo the study procedures and assessments described for Day 1 (Visit 2) before randomization ([Table 4](#)). Assessments conducted before randomization will be considered baseline assessments. Qualified patients who meet the entry criteria including HAM-D-17 score ≥ 24 , CGI-S score ≥ 5 , and QIDS-SR-16 score ≥ 19 will be randomly assigned in a 1:1:1 ratio to 1 of the 3 treatment arms:

- **Treatment A:** Patients will receive AZD6765iv 50 mg (total dose) intravenously once per dosing day at the study site. The infusion will be a

final volume of 100 mL given at an infusion rate of 1.67 mL/min (0.833 mg/min) over 60 minutes.

- **Treatment B:** Patients will receive AZD6765iv 100 mg (total dose) intravenously once per dosing day at the study site. The infusion will be a final volume of 100 mL given at an infusion rate of 1.67 mL/min (1.667 mg/min) over 60 minutes.
- **Treatment C:** Patients will receive placebo (0.9% saline) intravenously once per dosing day at the study site. The infusion will be a final volume of 100 mL given at an infusion rate of 1.67 mL/min over 60 minutes.

During Week 1, all patients will receive 3 infusions on non-consecutive days. After Infusion 1 (Visit 2), patients will remain on site for at least 3 hrs after the end of infusion. Starting from Infusion 2 (Visit 3), patients will remain on site for at least 1 hr after the end of infusion. Prior to release from the site during every visit, patients must demonstrate stable vital signs and will be questioned about any AEs being experienced. To ensure safety, all patients must refrain from driving and operating heavy machinery for the remainder of the day after infusions 1, 2, and 3 (Week 1). Patients who are unaccompanied by a driver will be provided transportation to their home.

Patients should be semi-recumbent in a bed or reclining chair such that their feet are at the same level as their torso during the iv infusion. Patients will receive multiple infusions of AZD6765 (50 mg or 100 mg) or placebo during the treatment period. For visits with a scheduled infusion and MADRS assessment, the MADRS assessment should be given prior to the infusion.

Blood samples will be collected for PK analysis at specified visits during Weeks 1, 3, 6, and 12 (see [Table 9](#) for blood sampling schedule for all patients during the study).

This study includes the option for randomized patients to participate in optional exploratory genetic research and optional biomarker analysis, where permitted. A 9 mL sample of blood will be collected from qualified patients who have also provided consent for optional exploratory genetic research. The blood sample for genetic research will be collected anytime after a patient has qualified for the study, but it is preferred that collection be done at the baseline/randomization visit (Visit 2, Day 1). The serum sample for biomarker analysis will be collected at baseline/randomization visit (Visit 2, Day 1) and at Visit 13.

Weeks 2 and 3: Visits 5 to 10 (Days 8 to 21, Infusions 4 to 9)

During Weeks 2 through 3, all patients will receive 3 infusions per each week on non-consecutive days ([Table 4](#)). Each infusion will be given over 60 minutes.

At designated visits when the QIDS-SR-16 is administered, it must always be done prior to any other procedure in a quiet room without staff input as specified. After medical clearance and confirming negative urine pregnancy test, urine drug screen, and confirmation that the

patient is taking no prohibited concomitant medications, MADRS, CGI-S, CGI-I, HAM-A, S-STS and CogState will be administered prior to infusion during the visits specified on [Table 4](#). The CADSS and C-SSRS will be administered after the infusion. The S-STS self report version must be reviewed by the investigator during the C-SSRS interview and signed by the investigator.

During Weeks 2 and 3, patients will remain on site for at least 1 hour from the end of infusion (ie, up to T₂).

Patients must report by telephone any AEs that occur after the first infusion (Infusion 1 after randomization [Week 1]).

Weeks 4, 5, and 6: Visits 11 to 13 (Days 22 to 42, Infusions 10 to 12)

During Weeks 4 through 6, all patients will receive 1 infusion per week (Visit 11 [Infusion 10], Visit 12 [Infusion 11], and Visit 13 [Infusion 12]) ([Table 4](#)). Visit 11 (Infusion 10) must occur 7 days (± 2 days) after Visit 10 (Infusion 9). All efforts should be made to complete the infusions on the same day of the week allowing for a 7-day interval between infusions; however, if this is not possible, a visit window of ± 2 days is permitted (minimum interval of 5 days and maximum interval of 9 days). The QIDS-SR-16, MADRS, CGI-S, CGI-I, HAM-A, S-STS and CogState will be administered prior to infusion during the visits specified in [Table 4](#). The CADSS and C-SSRS will be administered after the infusion. The S-STS self report version must be reviewed by the investigator during the C-SSRS interview and signed by the investigator.

During Weeks 4 through 6, patients will remain on site for at least 1 hour from the end of infusion (T₂).

At Week 6, a 2 mL serum sample will be collected from qualified patients who have also provided consent for optional exploratory biomarker research. The serum sample will be collected prior to the start of infusion.

Weeks 7 through 12: Visits 14 to 16 (Infusions 13 to 15)

During Weeks 7 through 12, all patients will receive 1 infusion every other week beginning on Week 8. This corresponds to Visit 14 (Infusion 13), Visit 15 (Infusion 14), and Visit 16 (Infusion 15) ([Table 4](#)). All efforts should be made to complete the infusions at 14-day intervals during this period. However, a minimum interval between infusions of 10 days and a maximum of 18 days must be observed.

The QIDS-SR-16, MADRS, CGI-S, CGI-I, S-STS, and CogState will be administered prior to infusion during the visits specified on [Table 4](#). The CADSS and C-SSRS will be administered after the infusion. The S-STS self report version must be reviewed by the investigator during the C-SSRS interview and signed by the investigator.

During the infusion days in Weeks 8 through 10, patients will remain on site for at least 1 hour after the end of infusion (T₂); at Week 12 (Visit 16), patients will remain on site for at least 3 hours after the end of infusion (T₄).

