- ^h A negative urine pregnancy test result is required prior to each dose of IP. Pregnancy tests will be administered and processed at the study site.
- ⁱ These measures will always be administered **prior to** any IP infusion.
- ^j At the screening visit, practice CogState is administered for training. The tests should be given twice (or more frequently if required to assure complete understanding of the requirements of each task).
- ^k CADSS will be administered at designated visits **after** infusion.
- ^l Patients must remain on site at randomization and the last infusion visit for at least 3 hours after the end of the infusion and at least 1 hour after the end of infusion at other scheduled infusions. Patients should be queried about any AEs and assessed for ability to leave the clinic, including their ability to drive or access to alternative transportation (see Section 5.1), prior to dismissal from the clinic at each infusion.
- ^m Weeks 1 through 3 post randomization-dose administration 3 times a week; Weeks 4 through 6 – dose administration once weekly; Weeks 8, 10, and 12 – dose administration once weekly. No drug administration will take place on Week 7, Week 9, and Week 11.

Figure 1Dosing flow chart

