6.2.2.2 Sheehan Suicide Tracking Scale (S-STs) Self report form

The S-STs is a prospective, patient self-report or clinician-administered rating scale that tracks suicidal ideation and behaviors and has been shown to be sensitive to clinical change with treatment ([Coric et al 2009](#), [Khan et al 2011](#)).

Only the self-report portion of the scale will be used in this study, which must be reviewed and signed by the investigator prior to conducting the C-SSRS interview. The S-STs will be administered at designated visits prior to the infusion. Note that the C-SSRS should be administered after the infusion.

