6.2.2.6 Columbia-Suicide Severity Rating Scale (C-SSRS)

The C-SSRS is a unique, simple and short method of assessing both behavior and ideation that tracks all suicidal events, and provides a summary of suicidality (Posner et al 2007). It assesses the lethality of attempts and other features of ideation (frequency, duration, controllability, reasons for ideation and deterrents), all of which are significantly predictive of completed suicide. The C-SSRS must be administered after each infusion and prior to discharging the patient from the clinic.

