6.3 Efficacy

6.3.1 Sequence of clinical rating assessments

Table 4 lists all clinical and laboratory assessments to be conducted at the screening visit and all subsequent visits. The following “priority order” among clinical ratings will be in effect for all visits after the screening visit.

Pre-infusion

- QIDS-SR-16
- S-STS (self report)
- MADRS
- HAM-A
- SDS
- CGI-S
- CGI-I
- CogState

Post-infusion

- C-SSRS (conducted by the investigator after reviewing and signing S-STS during visits when both instruments are used)
- CADSS

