6.3.3 Procedures for collecting patient reported outcomes (PRO)

Appropriate procedures for minimizing bias and enhancing compliance will be followed throughout the study. To ensure this, a study coordinator at each study site will be responsible for the PRO evaluation and a standardized procedure for the administration of the PRO questionnaires will be applied. The patient will complete the questionnaires independently, so that the responses reflect the patient’s perception and views rather than those of family, friends, staff, or others.

Each study site will have a designated quiet space in the clinic for the patients to complete the questionnaires at each visit. The questionnaires should be completed prior to other examinations, before there are substantial professional encounters with transmission of information, such as disease status. Such information may influence the answers that the patients provide on questionnaires. Training will be provided to study personnel to ensure the data quality through the standardized administration of the PRO questionnaires.

The QIDS-SR-16 and S-STS must both be administered prior to the infusion at designated visits.

The PROs of QIDS-SR-16 and SDS are discussed in Sections [6.2.2.1](#) and [6.3.2.2](#), respectively.

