Worsening symptoms of the primary study condition (ie, MDD) should not be recorded as an AE. However, if hospitalization results from worsening psychiatric symptoms, the hospitalization should be recorded as an SAE in the eCRF.

Study drug abuse is an SAE, even when there are no symptoms or additional AEs, and should be reported according to the guidelines in Section 6.4.4. Misuse of IP is an AE, but is not considered an SAE unless accompanied by serious sequelae.

Should an overdose of IP occur, it must be reported in accordance with the procedures described in Section 13.2. An overdose associated with symptoms must be reported as an AE, while an overdose without associated symptoms, must be reported only on the separate AstraZeneca Clinical Study Overdose Report Form.

Suicidality

Any patient who, based on the investigator's judgment, poses an imminent risk of suicide should be discontinued from the study (see Section 5.8 and Section 5.9). All efforts should be taken to minimize the risk of suicide and the investigator should carefully monitor the

patient. If during the course of the study, a patient shows evidence of serious suicidality (for example warranted by a scoring of 4 or 5 on the C-SSRS), the patient should be referred to their attending psychiatrist, a local emergency room etc. for further evaluation to see if they are safe to continue in the study. The site should have the ability to direct any patient that requires emergency hospitalization to an emergency room or inpatient psychiatric unit that is within a 50 mile radius of the site. In addition, the patient should be able to contact someone at the site 24 hours per day should they have serious worsening of their condition.

Suicide and attempted suicide, irrespective of the method, but occurring in connection with the use of IP, should be reported as AEs (serious or nonserious). This event should be identified as suicide or attempted suicide, and the method of the suicide or attempt should be provided. If an attempted suicide meets the criteria for an SAE, the event must be reported according to the guidelines in Section 6.4.4. Strong suicidal thoughts should also be regarded as AEs.

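### Minor: at the infusion visits with an S-STS, the completed suicidality self-report need not be read by the investigator before that day's dose, and the protocol gives two different times for the review

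*Protocol*

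**What the plan says.** The order of the two suicidality instruments around the infusion is consistent throughout the Protocol. Section 6.3.3 says: "The QIDS-SR-16 and S-STS must both be administered prior to the infusion at designated visits". Table 4, footnote i, and Section 3.1.2 agree. The C-SSRS comes afterwards; Section 6.2.2.6 says: "The C-SSRS must be administered after each infusion and prior to discharging the patient from the clinic".

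The time at which the investigator reads the S-STS is given in two ways:

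- Section 3.1.2, in each of its paragraphs for Weeks 2 and 3, Weeks 4 to 6 and Weeks 7 to 12: "The S-STS self report version must be reviewed by the investigator during the C-SSRS interview".
- Section 6.2.2.2, on the self-report form: "which must be reviewed and signed by the investigator prior to conducting the C-SSRS interview". Section 6.3.1 agrees in its post-infusion list: "C-SSRS (conducted by the investigator after reviewing and signing S-STS", at visits that use both instruments.

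Section 6.4.3 sets out the response to suicidality. A patient who in the investigator's judgement "poses an imminent risk of suicide should be discontinued from the study". A patient who shows evidence of serious suicidality is referred "for further evaluation to see if they are safe to continue in the study".

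**The concern.** The S-STS is a dedicated suicidality form, and at these visits the patient has finished it before the dose is given. The only mandatory moment for the investigator to read it is linked to an interview that follows the dose. Section 6.4.3 asks the investigator to judge whether a patient is at imminent risk or safe to continue, so information already on paper may reach that judgement only after another infusion.

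The two wordings are also both mandatory. A site that reads the form only in the course of the interview complies with Section 3.1.2 and, read literally, departs from Section 6.2.2.2.

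What is at stake is the order of steps within one clinic visit. No estimate or test is involved.

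**Working it through.** No planned figure bears on this point, so the check compares the schedule with the text and adds one piece of timing arithmetic.

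**Which visits.** Infusions after the first are given at Visits 3 to 16, which is 14 (Table 4). The S-STS row is marked at Visits 1, 2, 5, 8, 11, 12, 13, 14, 15, 16 and Week 14.

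- Infusion visits after the first with an S-STS: 5, 8, 11, 12, 13, 14, 15, 16 = 8.
- Infusion visits after the first without one: 3, 4, 6, 7, 9, 10 = 6. Check: 8 + 6 = 14.
- Visit 2 also has the S-STS before and the C-SSRS after its infusion. The review sentence of Section 3.1.2 does not appear under Week 1, so only Sections 6.2.2.2 and 6.3.1 govern the review there. With Visit 2, 8 + 1 = 9 infusion visits carry an S-STS.
- Screening and Week 14 have an S-STS but no infusion.

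**When the review falls, counted from the start of the infusion.** The infusion lasts 60 minutes (Section 5.5.2).

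- Earliest post-infusion C-SSRS, and so earliest required review under Section 3.1.2: 60 minutes.
- The review must be done by discharge, because the C-SSRS must precede it. Table 4, footnote l, keeps patients on site "at least 1 hour after the end of infusion at other scheduled infusions", so release is possible from 60 + 60 = 120 minutes at Visits 5, 8 and 11 to 15 (seven visits).
- At Visit 16 the stay is at least 3 hours, so release is possible from 60 + 180 = 240 minutes.
- No maximum stay is stated, so these are the earliest release times and do not cap the delay.

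Under Sections 6.2.2.2 and 6.3.1 the review may fall before or after the infusion, as long as it precedes the C-SSRS.

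**Whether a pre-dose reading is required anywhere.** Sections 3.1, 3.1.2, 6.2.1.2, 6.2.2.2, 6.2.2.6, 6.3.1, 6.3.3, 6.4.3 and 6.4.9.6 were compared. None requires the investigator to read the S-STS before that day's infusion, and none forbids it. At screening the Protocol is more explicit: in Section 6.2.1.1 the investigator reads the S-STS answers, asks about any ideation reported, completes the C-SSRS and only then decides on enrolment.

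**What else the site knows before the dose.** MADRS, CGI-S and CGI-I are scheduled before the infusion at all eight visits. The QIDS-SR-16, which has a suicidal-ideation domain (Section 6.2.2.1), also precedes it at Visits 8, 13 and 16.

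**The case against.** The strongest reply is that this is one practical step described twice. An investigator who opens the C-SSRS interview by reading and signing the S-STS meets the evident intent of both wordings, and the screening visit pairs the two instruments in the same way. On this view the difference between the sections is a wording clean-up. That part of the reply largely stands; the discrepancy alone would be slight.

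The second reply is that a pre-dose reading triggers nothing defined. The S-STS does not decide dosing, and its efficacy objective is exploratory. The example of serious suicidality in Section 6.4.3 is a C-SSRS score of 4 or 5. Clinician ratings precede the dose, the patient stays on site, and the C-SSRS is done before discharge, so the safeguards still operate the same day. Section 6.4.3 also imposes a general duty to monitor the patient carefully. All of this stands, and it limits the benefit. It does not remove the point: Sections 6.3.2 and 6.3.2.1 allow a delegate to make the ratings and a nurse to administer the MADRS, so those ratings do not ensure that the investigator has seen the patient's own report.

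A third reply concerns the remedy. Reading the form near the MADRS could influence the primary rating, and a rule written only around the infusion would leave screening and Week 14 without one. Both are fair, and the rule proposed below covers them.

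A reader might infer more: that the Protocol forbids an earlier look, that patients at imminent risk will be dosed, or that a suicidality check before every dose has been left out. The documents do not support these readings. An earlier look is open to any site. Six other infusions after the first have no S-STS by design. Section 1.4 reports no treatment-group difference in suicidal ideation or behaviour on the C-SSRS, and no harm from the delay can be shown from the text.

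**Conclusion.** The point holds as a minor, optional improvement. At Visits 5, 8 and 11 to 16 the S-STS is completed before the infusion, its mandatory review is timed in two different ways, and neither ties it to that day's dose. Strict compliance with Section 3.1.2 allows dosing while the form is unread.

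The size is 8 of the 14 infusions after the first, with the required review under Section 3.1.2 at least 60 minutes after the infusion starts. How many patients would have a relevant answer on an unread form cannot be derived from the Protocol. No endpoint, power or error rate is affected. The conclusion rests on Table 4 and the cited sections as they stand; site instructions outside the Protocol might already require an earlier reading.

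**What to change.** Use one rule in Sections 3.1.2, 6.2.2.2 and 6.3.1:

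> At every infusion visit with an S-STS (Visits 2, 5, 8 and 11-16), the investigator reviews and signs the S-STS before the infusion starts and after the MADRS and CGI ratings for that visit are complete, and refers to it again at the post-infusion C-SSRS. At visits without an infusion (screening, Week 14), the S-STS is reviewed and signed before the C-SSRS interview.

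In Section 6.3.1, list the review among the pre-infusion steps, after the CGI ratings. Placing it there keeps the self-report from influencing the MADRS. The instruments, the visits and the timing of the C-SSRS do not change, and the response to a positive answer stays with the investigator under Section 6.4.3.

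The cost is five text edits: one sentence in each of three paragraphs of Section 3.1.2, one in Section 6.2.2.2 and one list entry in Section 6.3.1. An investigator must be available for a brief review (about a minute, as an assumption) before the infusion at nine visits. In Weeks 2 and 3, Section 3.1.2 already requires medical clearance before dosing.

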3.1.3 Follow-up Visit

As implemented by Amendment 2, patients will be scheduled for a 14 (\pm 4 days)-day follow-up visit (Week 14) from last dosing to collect laboratory measurements and other assessments as detailed in [Table 4](#), including CogState.

Patients who have completed the infusions prior to implementation of Amendment 2, but are still within the 14 (\pm 4 days)-day window from last dosing, will have a 14 (\pm 4 days)-follow-up visit (Week 14), regardless of whether they have completed assessments scheduled for Week 13 (Visit 17) under the previous protocol amendment. Patients who have completed assessments scheduled for Week 13 (Visit 17) under the previous protocol amendment do not need to repeat any laboratory assessments.

Patients who have completed the infusions and are outside the 14 (\pm 4 days)-day window from last dosing at the time of implementation of Amendment 2 will be considered complete. These patients may return to the site for an unscheduled follow-up visit at the discretion of the investigator.

Table 4 Study assessments through the treatment period

	Enroll- ment		Treatment Period															
	Screen/ Washout	R															EOT	Follow- up ^b
Visit	1 ^a	2	3	4	5	6	7	8	9	10	11	12	13	14	15	16		
Infusion		1	2	3	4	5	6	7	8	9	10	11	12	13	14	15		
Week	-6 to -1	Week 1			Week 2			Week 3			W4	W5	W6	W8	W10	W12	W14	
Day (±x days)	-42 to -1	non-consecutive days									(±2)	(±2)	(±2)	(±4)	(±4)	(±4)	(±4)	
Informed consent	X																	
Inclusion/exclusion criteria	X	X																
Demography	X																	
Psychiatric (including number of depressive episodes) and family history	X																	
Prior and concomitant medication	X	X	X	X	X	X	X	X	X	X	X	X	X	X	X	X	X	
Medical and surgical history	X																	
Alcohol and drug history	X																	
ATHF	X																	
Employment status	X	X															X	
Vital signs (supine)	X	X ^c	X ^c	X ^c	X ^c	X ^c	X ^c	X ^c	X ^c	X ^c	X ^c	X ^c	X ^c	X ^c	X ^c	X ^c	X ^c	
Orthostatic BP ^d		X	X	X	X	X	X	X	X	X	X	X	X	X	X	X		
Physical examination		X															X	

Table 4 Study assessments through the treatment period

	Enroll- ment		Treatment Period															
	Screen/ Washout	R															EOT	Follow- up ^b
Visit	1 ^a	2	3	4	5	6	7	8	9	10	11	12	13	14	15	16		
Infusion		1	2	3	4	5	6	7	8	9	10	11	12	13	14	15		
Week	-6 to -1	Week 1			Week 2			Week 3			W4	W5	W6	W8	W10	W12	W14	
Day (±x days)	-42 to -1	non-consecutive days									(±2)	(±2)	(±2)	(±4)	(±4)	(±4)	(±4)	
Weight, height, BMI	X	X															X	
Digital 12-lead ECG ^d	X	X		X						X			X			X		
Hematology	X	X											X				X	
Clinical chemistry ^c	X ^f	X											X				X	
Glucose	X	X															X	
HgbA _{1c}	X																X	
HIV, HBsAg, and HCV	X																	
MINI	X																	
HAM-D-17	X	X																
Serum pregnancy for all females ^g	X																X	
Urine Pregnancy for WOCBP ^h		X	X	X	X	X	X	X	X	X	X	X	X	X	X	X		
Urinalysis	X	X											X				X	
Urine drug screen	X																	

Table 4 Study assessments through the treatment period

	Enroll- ment	Treatment Period																
	Screen/ Washout	R															EOT	Follow- up ^b
Visit	1 ^a	2	3	4	5	6	7	8	9	10	11	12	13	14	15	16		
Infusion		1	2	3	4	5	6	7	8	9	10	11	12	13	14	15		
Week	-6 to -1	Week 1			Week 2			Week 3			W4	W5	W6	W8	W10	W12	W14	
Day (±x days)	-42 to -1	non-consecutive days									(±2)	(±2)	(±2)	(±4)	(±4)	(±4)	(±4)	
AEs	X	X	X	X	X	X	X	X	X	X	X	X	X	X	X	X	X	
Prohibited medication washout period (see Section 5.6.1)	X																	
PK sampling (AZD6765 levels)		X								X			X			X		
QIDS-SR-16 ⁱ	X	X						X					X			X	X	
S-STS ⁱ	X	X			X			X			X	X	X	X	X	X	X	
MADRS ⁱ		X	X	X	X			X			X	X	X	X	X	X	X	
HAM-A ⁱ		X											X			X		
SDS		X											X			X	X	
CGI-S ⁱ	X	X			X			X			X	X	X	X	X	X	X	
CGI-I ⁱ					X			X			X	X	X	X	X	X	X	
CogState ⁱ	X ^j	X											X				X	
C-SSRS	X	X	X	X	X	X	X	X	X	X	X	X	X	X	X	X	X	

[figure not shown]
Table 4 Study assessments through the treatment period

	Enroll- ment		Treatment Period															
	Screen/ Washout	R															EOT	Follow- up ^b
Visit	1 ^a	2	3	4	5	6	7	8	9	10	11	12	13	14	15	16		
Infusion		1	2	3	4	5	6	7	8	9	10	11	12	13	14	15		
Week	-6 to -1	Week 1			Week 2			Week 3			W4	W5	W6	W8	W10	W12	W14	
Day (±x days)	-42 to -1	non-consecutive days										(±2)	(±2)	(±2)	(±4)	(±4)	(±4)	(±4)
CADSS ^k		X											X					
Biomarker sampling (optional)		X											X					
PGx sampling (optional)		X																
IP infusion ^l		X ^m	X ^m	X ^m	X ^m	X ^m	X ^m	X ^m	X ^m	X ^m	X ^m	X ^m	X ^m	X ^m	X ^m	X ^m		

AE adverse event; ATHF Antidepressant Treatment History Form; BMI body mass index; BP blood pressure; CADSS Clinician Administered Dissociative States Scale; CGI-I Clinical Global Impression-Improvement; CGI-S Global Impression-Severity of Illness; C-SSRS Columbia-Suicide Severity Rating Scale; ECG electrocardiogram; EOT end of treatment period; HAM-A Hamilton Depression Rating Scale for Anxiety; HAM-D-17 Hamilton Rating Scale for Depression; HBsAg hepatitis B surface antigen; HCV hepatitis C virus; HIV human immunodeficiency virus; IP investigational product; MADRS Montgomery-Åsberg Depression Rating Scale; MINI Mini-International Neuropsychiatric Interview; PK pharmacokinetic; PRO patient-reported outcomes; QIDS-SR-16 Quick Inventory of Depressive Symptomology Self-Report 16-item scale; R randomization; SDS Sheehan Disability Scale; S-STS Sheehan Suicide Tracking Scale; WOCBP women of childbearing potential.

- ^a The screening visit can be completed over 2 days if agreed upon with medical advisor.
- ^b Patients who have completed assessments scheduled for Week 13 (Visit 17) under the previous protocol amendment and are still within the 14 (\pm 4 days)-day window from last dosing, will have a follow-up visit (Week 14), but laboratory assessments will not need to be repeated.
- ^c Vital signs will be measured at time 0 (T_0 before infusion, within 1 hour before infusion is acceptable), at the end of infusion (T_1), and either at least 1 hour (T_2) after the end of infusion (all indicated visits, except for Visits 2 and 16), or, at least 3 hours (T_4) after the end of infusion (applies to Visits 2 and 16).
- ^d Orthostatic BP will be measured at T_0 (within 1 hour before infusion is acceptable) and either at least 1 hour (T_2) after the end of infusion (all indicated visits except for Visits 2 and 16), or at least 3 hours (T_4) after the end of infusion (applies to Visits 2 and 16).
- ^e ECGs will be measured at T_0 (before infusion, within 1 hour before infusion is acceptable) and T_1 (end of infusion) at Visit 2, and at T_1 only for Visits 4, 10, 13, and 16.
- ^f Serum lithium concentrations for patients receiving lithium as adjunct therapy for the treatment of their MDD will be measured as part of the clinical chemistry assessment.
- ^g Blood sampling for FSH for all post-menopausal women under 50 years of age.
- ^h A negative urine pregnancy test result is required prior to each dose of IP. Pregnancy tests will be administered and processed at the study site.
- ⁱ These measures will always be administered **prior to** any IP infusion.
- ^j At the screening visit, practice CogState is administered for training. The tests should be given twice (or more frequently if required to assure complete understanding of the requirements of each task).
- ^k CADSS will be administered at designated visits **after** infusion.
- ^l Patients must remain on site at randomization and the last infusion visit for at least 3 hours after the end of the infusion and at least 1 hour after the end of infusion at other scheduled infusions. Patients should be queried about any AEs and assessed for ability to leave the clinic, including their ability to drive or access to alternative transportation (see Section 5.1), prior to dismissal from the clinic at each infusion.
- ^m Weeks 1 through 3 post randomization-dose administration 3 times a week; Weeks 4 through 6 – dose administration once weekly; Weeks 8, 10, and 12 – dose administration once weekly. No drug administration will take place on Week 7, Week 9, and Week 11.

Figure 1Dosing flow chart

